2.2.3. Treatment Period

Subjects will undergo study treatment duration of 12 weeks of ¹⁴N sodium nitrite three times daily. This is considered appropriate to demonstrate the potential effects of nitrite on the cardiometabolic and hormonal disturbances in overweight/obese adults with metabolic syndrome and hypertension.

2.2.4. Safety Monitoring:

Subjects will be evaluated with outpatient two hour post-dose safety assessments at baseline and at 12 weeks following completion of the 12-week treatment. Every other week safety visits will occur to assess adverse events (AE) and interval histories in the Endocrinology and Metabolism Research Center (EMRC) at Montefiore Hospital) for visits 6, 8, 10, 12 and 14. Visits 5, 7, 9, 11, 13 and 15 will occur by phone. The in person safety visits will include brief physical exams, methemoglobin level, interval histories medication compliance review, symptom review and dispensing of study drug. The phone visit will include symptom review, assessing adverse events and interval histories.

In addition to these formal evaluations, subjects will be encouraged to immediately contact the study investigator and/or the study coordinator with questions, concerns, or to report new symptoms that occur during their study participation. If there are particular concerns that need addressed sooner than the every other week in-person visit, the subject will be asked to return to the EMRC as soon as possible for evaluation. If appropriate, based upon the evaluation, medical treatments will be provided to subjects, including appropriate referral to physicians or other services at the UPMC.

2.2.5. Medication Compliance

Subjects will self-administer their first dose of study medication under supervision of the physician investigator in the outpatient CTRC during Day 1 (Visit 4- First Drug Dose visit), following completion of all baseline clinic assessments. Subjects will also be dispensed their study medication for home use. Subjects will return the previously dispensed study medication at each every other week study visit thereafter, and medication compliance will be assessed. The study investigator and/or the study coordinator will review the daily diary. In the event that the compliance rate is < 80%, subjects will be re-educated on medication compliance. If medication compliance repeatedly falls outside of the acceptable range, the study investigators will discuss subject eligibility for continued participation in the study.

2.2.6. Medication Accountability

The study investigators or the study coordinator will document the amount of study drug dispensed from UPMC-IDS. The study drug accountability records will be maintained at UPMC-IDS throughout the course of the clinical trial.

2.3 STUDY ASSESSMENT

The complete study assessment and procedures are outlined in Table 1. During the treatment period, a variance of 7 days will be allowed to accommodate for scheduling needs.

2.3.1. Screening Procedures

Visit 1 (Screening)

The outpatient fasting screening will take place in the Montefiore Clinical and Translational Research Center (CTRC) or the Endocrinology Metabolism Research Center (EMRC) at the UPMC Montefiore Hospital. Subjects will be asked to fast for 8 hours before coming in for the screening blood work.

- Obtain written informed consent.
- Obtain waist and hip circumferences.
- Complete history and physical examination to include body weight, height, and menstrual history in females.
- Metabolic syndrome screening blood draw: triglycerides, HDL and fasting glucose.
- TSH level to rule out uncontrolled hypothyroidism (TSH >8 mIU/mL)
- Hemoglobin and hematocrit to assess for anemia (hemoglobin <11.0); If the value is within IRB guidelines, the subject may proceed with full protocol implementation. If the hemoglobin is less than required, a stat CBC will be sent to chemistry. If the central lab value is within range or the subject is determined to have thalassemia trait per the IRB "Blood Withdrawal Guidelines for Research Subjects", the subject may proceed with full protocol implementation.
- Blood pressure and other vital signs.

Screening evaluations will include triglycerides, HDL, glucose, TSH, and hemoglobin and hematocrit by the Presbyterian Hospital clinical automated testing lab and are to be covered by research funds. The total volume of blood drawn is approximately 1 Tablespoon (15 mL). If laboratory results exclude elevated TSH (>8 mIU/mL) and low hemoglobin (<11.0 g/dL) and blood pressure measurement confirms hypertension, the subject will be called to arrange the baseline assessments.

Subjects who fail to meet applicable inclusion/exclusion criteria based upon the results of the screening assessment will be excluded from further study participation.

Visit 2 (First Baseline Assessment Visit)

Subjects will be scheduled for an outpatient fasting Vascular CTRC and EMRC visit within 4 weeks of screening. Subjects will be asked not to drink or eat anything other than plain water for 8 hours prior to their arrival for this visit.

- Body weight
- Pulse Wave Velocity (PWV)
- Flow Mediated Dilation (FMD)
- Carotid Intima-Media Thickness (IMT)
- Urine pregnancy test in females of child-bearing potential (i.e. women who are not at least 1 year post-menopausal or who have not undergone a surgical sterilization procedure)
- Light breakfast snack in CTRC
- Whole body DEXA scan
- Exercise testing

- 24-hour ambulatory blood pressure monitor (ABPM) placement *This may also be placed at Visit 3 if a monitor is not available when a participant comes in for Visit 2.*
- AE assessment

Visit 3 (Second Baseline Assessment Visit)

Visit 3 involves a percutaneous muscle biopsy. To prevent acute effects of exercise on muscle mitochondria function, the visit will occur 2-7 days after Visit 2. This visit will take place at the MUH-CTRC. Subjects will be asked not to drink or eat anything other than plain water for 8 hours prior to their arrival for this visit.

- History and physical examination including vital signs, body weight, and menstrual history in females
- Urine pregnancy test in females of child-bearing potential (i.e. women who are not at least 1 year post-menopausal or who have not undergone a surgical sterilization procedure)
- Fasting blood draw to include: estradiol level in females sent to Esoterix; HbA1C, CBC, creatinine, AST and ALT and lipid profile sent to Presbyterian Hospital clinical automated testing lab; research blood for ICAM-1, VCAM-1, e-Selectin, CRP, adiponectin, leptin, uric acid, PAI-1, IL-6, TNF- α , and platelet sample (approximately 3 Tablespoons of blood)
- 72-hour dietary food recall
- Indirect calorimetry
- Percutaneous muscle biopsy
- Hyperinsulinemic euglycemic clamp (22 Tablespoons of blood)
- Meter blood sugar, blood pressure, breathing rate, and heart rate will be performed 30 minutes after completion of the clamp test to make sure they are returning to baseline before discharge home.
- Regular meal after completion of clamp
- Return blood pressure monitor and cuff for download
- AE assessment

The total volume of blood drawn is approximately 25 Tablespoons (375 mL).

2.3.2. Treatment Period and Monitoring

Visit 4 (Day 1: First Drug Dose Visit)

Administration of the first dose of study drug will occur within 1-4 weeks following completion of all baseline assessments. Subjects will be asked not to drink or eat anything other than plain water for 8 hours prior to their arrival for this visit. The fasting visit will take place in the outpatient CTRC.

- Body weight and temperature in all subjects and menstrual history in females
- Urine pregnancy test in females of child-bearing potential (i.e. women who are not at least 1 year post-menopausal or who have not undergone a surgical sterilization procedure)
- Subjects will receive their first dose of study drug as follows:
 - ^{14}N sodium nitrite 40 mg
- Blood pressure, MAP and heart rate will be measured in triplicate after approximately 30 minutes of rest and quiet in the CTRC to ensure blood pressures are at a steady state before taking the study drug (baseline) and then every 15 minutes for the 2 hours post-drug administration
- Methemoglobin level by finger probe at 0 (trough prior to sodium nitrite), 0.5, 1 and 2 hours post-drug administration

- Research blood samples for: plasma nitrate and nitrite concentrations, red cell iron-nitrosyl-hemoglobin and platelet studies at 0 (trough), 0.5 and 2 hours post-drug administration
- AE assessment
- Light breakfast snack
- Provide dosing diary cards and a 11-17 day supply of study drug so there is enough daily drug to get them to their next scheduled Visit 6
- Return completed 72 hour dietary recall forms

The total volume of blood drawn is approximately 3 Tablespoons (or 48 mL).

There is a rare possibility that a subject will have a high methemoglobin level or will have a low blood pressure from their study drug dose during this visit or future study visits. If this happens, their study nitrite drug dose will be lowered so that they receive half the dose of the nitrite (20 mg sodium nitrite three times daily). They will be asked to undergo a repeat of safety monitoring for blood pressure, breathing rate and heart rate before taking the medicines and then every 15 minutes for 2 hours after taking the study medications, methemoglobin level by a finger probe, research blood and storage samples and blood samples for platelet mitochondrial function that will be drawn before, 0.5, 1 and 2 hours after the lowered dose of study medication are administered (as above). The total volume of blood drawn is approximately 3 Tablespoons. If they still have a high methemoglobin or low blood pressure on the lower dose, their participation in the study will be discontinued.

Visits 5-15 (Weeks 1 through 11):

Participants will have every other week in-person EMRC safety visits and phone visits on alternate weeks, starting with week 1 (Visit 5) if no dose limiting adverse events occur (as defined in protocol based on MAP and MetHb levels). Phone visits will take place on Visit 5, 7, 9, 11, 13 and 15.

During Visits 6, 8, 10, 12, and 14 (Weeks 2, 4, 6, 8, and 10 on study drug), the subjects will return every other week \pm 7 days to the EMRC in Montefiore Hospital of UPMC for a safety visit, which will take approximately 1-1 ½ hours for:

- Subjects will be seated in the EMRC and given their daily dose of morning study drug or second/midday dose (depending on time of scheduled visit)
- Brief physical exam
- 0.5 hours after taking their study drug, 3 automated blood pressure, HR and MAP measurements will be taken by the subject with 5 minutes intervals between measurements
- Assess adverse events (AE) and medication compliance
- Obtain methemoglobin by co-oximetry and research blood for plasma nitrate and nitrite levels and a sample for storage
- Provide a 14 +/- 3 day supply of study drug

During Visits 5, 7, 9, 11, 13, and 15 (Weeks 1, 3, 5, 7, 9, and 11 on study drug or every other week), we will contact the subject by phone for a safety visit to assess interval histories and assessment of adverse events (AE), which will last about 10 minutes.

The total volume of blood drawn at the in-person safety visits is approximately 1 1/8 Tablespoons (or 16 mL). At the Week 6 (Visit 10) visit, body weight, and menstrual history in females and urine pregnancy test in females of child-bearing potential (i.e. women who are not at least 1 year post-

menopausal or who have not undergone a surgical sterilization procedure) and a blood sample for platelet studies will be performed. Total blood volume for Visit 10 is about 1 2/3 Tablespoons (or 24 mL).

At Week 10 (Visit 14), a hemoglobin and hematocrit will be drawn to screen for anemia. If hemoglobin is less than 11 g/dL, iron supplementation (ferrous sulfate 325 mg twice daily) will be recommended until study completion at Visit 18. A repeat hemoglobin and hematocrit will be repeated at Visit 18. If hemoglobin is $>$ or $=$ 11 g/dL, participation in this visit will occur. If hemoglobin $<$ 11 g/dL, continuation of iron supplementation will occur and the visit will be rescheduled within the permitted 7 day scheduling variance when the hemoglobin and hematocrit will again be repeated. Total blood volume for Visit 14 is about 1 1/3 Tablespoons (or 20 mL).

Visit 16 (Week 12: First Completion Assessment Visit)

Subjects will be scheduled for an outpatient fasting CTRC and Vascular CTRC visit for:

- Body weight in all subjects and menstrual history in females
- Waist and hip circumference measurements
- Pulse Wave Velocity (PWV)
- Flow Mediated Dilation (FMD)
- Carotid Intima-Media Thickness (IMT)
- Urine pregnancy test in females of child-bearing potential (i.e. women who are not at least 1 year post-menopausal or who have not undergone a surgical sterilization procedure)
- Whole body DEXA scan
- Exercise testing
- Light breakfast snack
- 24-hour ambulatory blood pressure monitor placement*This may also be placed at Visit 17 if a monitor is not available when a participant comes in for Visit 16.*
- 72-hour dietary food recall
- Assess AEs, review diary cards and medication compliance
- Provide remaining supply of study drug until scheduled Visit 18 Third Completion Assessment Visit (Week 12).

Visit 17 (Week 12: Second Completion Assessment Visit)

This fasting visit will take place at the CTRC or EMRC. Subjects will be asked not to drink or eat anything other than plain water for 8 hours prior to their arrival for this visit.

- Body weight and temperature will be measured in all and menstrual history in females
- Urine pregnancy test in females of child-bearing potential (i.e. women who are not at least 1 year post-menopausal or who have not undergone a surgical sterilization procedure)
- Subjects are asked to bring their morning dose of study drug to this visit for dosing as follows:
 - ^{14}N sodium nitrite 40 mg
- Blood pressure, MAP, and heart rate will be measured in triplicate after approximately 30 minutes of rest and quiet in the CTRC to ensure blood pressures are at a steady state before taking the study drug (baseline) and then every 15 minutes for the 2 hours post-drug administration
- Methemoglobin level by finger probe at 0 (trough prior to sodium nitrite), 0.5, 1 and 2 hours post-drug administration
- Research blood samples for plasma nitrate and nitrite concentrations, red cell iron-nitrosyl-hemoglobin and platelet studies at 0 (trough), 0.5 and 2 hours post-drug administration

- Assess for AEs during study testing
- Standard meal following completion of 2 hour post-drug administration blood draw
- 72-hour food recall forms will be collected if already completed
- Return blood pressure monitor and cuff for download

The total volume of blood drawn is approximately 4 Tablespoons (or 48 mL).

Visit 18 (Week 12: Third Completion Assessment Visit)

This visit involves a percutaneous muscle biopsy. To prevent acute effects of exercise on muscle mitochondria function, the visit will occur 2-7 days after Visit 16 (the exercise visit). Subjects will be asked not to drink or eat anything other than plain water for 8 hours prior to their arrival for this visit.

- History and physical examination, weight, and vital signs
- Urine pregnancy test in females of child-bearing potential (i.e. women who are not at least 1 year post-menopausal or who have not undergone a surgical sterilization procedure)
- Fasting blood draw to include basic labs of estradiol level (in females), HbA1C, and lipid profile; research blood for ICAM-1, VCAM-1, e-Selectin, CRP, adiponectin, leptin, uric acid, PAI-1, IL-6, TNF- α and a sample for storage (approximately 3 Tablespoons of blood)
- Subjects are asked to bring their morning dose of study drug to this visit for dosing prior to start of indirect calorimetry
- Indirect calorimetry
- Percutaneous muscle biopsy
- Hyperinsulinemic euglycemic clamp (22 Tablespoons of blood)
- Meter blood sugar, blood pressure, breathing rate, and heart rate will be performed 30 minutes after completion of the clamp test to make sure they are returning to baseline before discharge home.
- Regular meal after completion of clamp
- Medication compliance review
- AE assessment
- 72-hour food recall forms will be collected if not already returned
- All remaining study drug will be collected since the last dispensing of drug earlier in the week (at Visit 16)

The total volume of blood drawn is approximately 25 Tablespoons (370 mL).

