2.3.3. End of Trial and Follow-Up Period

Visit 19 (Week 16: Post Study Drug Telephone Assessment)

- Telephone assessment for interval histories and AEs.

Table 1. Study Assessment and Procedures

	Screening	Baseline			Treatment Period and Monitoring														FU
Visit	1	2	3	4	5	6	7	8	9	10	11	12	13	14	15	16	17	18	19
Week of Treatment	-	-4~-1	-4~-1	0	1	2	3	4	5	6	7	8	9	10	11	12	12	12	16
Day of Treatment	-	-28~-7	-28~-7	1	8	15	22	29	36	43	50	57	64	71	78	85	86-91	87-92	113
Time Window			V2 +2-7d		±7	±7	±7	±7	±7	±7	±7	±7	±7	±7	±7	±7		V16 +2-7d	±3
Visit Type	OP	OP	OP	OP	Phone	OP	Phone	OP	Phone	OP	Phone	OP	Phone	OP	Phone	OP	Phone	OP	Phone
Informed Consent / Eligibility Criteria	x																		
History & Physical Exam	x																		
Body Weight	x	x	x	x						x						x	x	x	
Waist and hip circumference	x															x			
Vital signs	x	x	x			x		x		x		x		x		x		x	
Menstrual History (in females)	x		x							x								x	
Screening Laboratory Profile	x																		
Urine Pregnancy Test (in females)		x	x	x						x						x	x	x	
Methemoglobin %				x		x		x		x		x		x			x		
Estradiol Level (in females)			x															x	
Research Labs			x	x		x		x		x		x		x			x	x	
Two Hour Safety Blood Sampling				x													x		
Two Hour HR, MAP, and BP Monitoring				x													x		
Hemoglobin & hematocrit														x					
Food Questionnaire			x														x		
Whole body DEXA Scan		x															x		
Pulse Wave Velocity		x															x		
Flow Mediated Dilation		x															x		
Carotid Intima-Media Thickness		x															x		
24-hour ABPM		x															x		
Hyperinsulinemic Euglycemic Clamp			x																x
Indirect Calorimetry			x																x
Muscle Biopsy			x																x
Exercise Testing		x															x		
Meal/snack		x	x	x													x	x	x
AE Assessment		x		x	x	x	x	x	x	x	x	x	x	x	x	x	x	x	x
Medication Compliance Review					x	x	x	x		x		x		x		x		x	
Interval History Assessment			x		x	x	x	x	x	x	x	x	x	x	x	x		x	x
Brief physical exam			x		x	x	x	x		x		x		x				x	

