- The frequency of monitoring that took place during the renewal intervals and/or the dates that data and safety monitoring was conducted.
- A summary of cumulative data related to unanticipated problems (including adverse events) including a determination of causality and whether the risk to benefit assessment has changed.
- If appropriate, a summary of pertinent scientific literature reports, therapeutic developments, or results of related studies that may have an impact on the safety of study participants or the ethics of the research study.
- A summary of the outcome of reviews conducted to ensure subject privacy and research data confidentiality.
- Final conclusions regarding changes to the anticipated benefit-to-risk assessment of the study participation and final recommendations related to continuing, changing, or terminating the study.

Stopping Rule:

For safety reasons, we propose to discontinue this study protocol once 2 subjects enrolled experience one of two of the following on repeat PK testing despite appropriate nitrite dose reduction as follows:

1. Methemoglobin greater than 5%. A nitrite dose reduction is proposed from 40 mg three times daily to 20 mg three times daily if this methemoglobin % is reached at any study visit. Two hour PK testing will be repeated on a separate day at the lower nitrite dose once two subjects have reached this initial methemoglobin threshold. If methemoglobin is greater than 5% on the lower nitrite dose, participation in the study for the subject will be discontinued.
2. Mean arterial pressure (MAP) decrease <55 mmHg, or if subject's baseline MAP is <60, and there is a decrease greater than or equal to 20% from their baseline (on the morning of receiving study drug). A nitrite dose reduction is proposed from 40 mg to 20 mg three times daily if this MAP threshold is reached. Two hour PK testing will be repeated on a separate day at the lower nitrite dose once two subjects have reached this initial MAP threshold. If MAP remains <55 mmHg or in the case of the subject with a baseline MAP <60, then if MAP decrease is greater than or equal to 20% from baseline on the lower dose, subject participation in the study will be discontinued.
3. Positive pregnancy test.

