4. In the event that the medication compliance rate is <80%, subjects will be re-educated on medication compliance. If medication compliance repeatedly falls outside of the acceptable range, the study investigators will discuss subject eligibility for continued participation in the study.

If an unexpected fatal event or any of the above three life-threatening events occur despite dose reduction, the study will be halted, until data review by investigators and the Data Safety Monitoring Board has rendered a final recommendation about study continuation.

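### Only one pregnancy test is scheduled between first dose and Week 12, leaving 42-day gaps; add the test at Visits 8 and 12 and state what a positive result does

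*Combined protocol and SAP*

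**What the plan says.** The visit text in Sections 2.3.1 and 2.3.2 and the Table 1 row "Urine Pregnancy Test (in females)" agree: urine pregnancy tests fall at Visits 2, 3, 4, 10, 16, 17 and 18. The one test on treatment before the completion visits is described as follows: "At the Week 6 (Visit 10) visit, body weight, and menstrual history in females and urine pregnancy test in females of child-bearing potential".

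Visits 6, 8, 12 and 14 are also in person. At each, the subject takes a dose under observation and receives more capsules ("Provide a 14 +/- 3 day supply of study drug"), with no pregnancy test listed. Visit 4 hands out the initial supply: "Provide dosing diary cards and a 11-17 day supply of study drug". Section 2.3 sets the window: "During the treatment period, a variance of 7 days will be allowed to accommodate for scheduling needs".

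Section 5.4.2 deals with a positive result under its Stopping Rule. Item 3 of the list reads in full "Positive pregnancy test". Items 1 (methemoglobin) and 2 (mean arterial pressure) each go on to say when the individual subject leaves the study; item 3 does not. The closing paragraph then says that if an unexpected death or "any of the above three life-threatening events occur despite dose reduction, the study will be halted", pending review by the investigators and the Data Safety Monitoring Board.

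**The concern.** A positive pregnancy test is on the protocol's own stopping list, but on schedule that item can act only when a test is done. As planned, a woman who becomes detectably pregnant soon after Visit 4 or Visit 10 could take nitrite three times daily for about six weeks, and collect drug twice in person, before the next scheduled test. The spacing also looks uneven. Three tests fall close together at Visits 16 to 18, when dosing is almost over, and Section 5.1.2 asks for a negative test within 24 hours before a DEXA scan whose risk it calls low.

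The second part concerns the instruction that follows a positive result. Staff who see one at Visit 10 have no stated action for that subject in the text available here, and the closing paragraph leaves open whether the event concerns her alone or the whole trial. More frequent testing makes this matter more, because false positives become slightly more likely.

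What is at stake is avoidable drug exposure in an unrecognised pregnancy, and a clear instruction for staff. Sample size, power and type I error are untouched.

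**Working it through.** **Inputs.** Table 1 gives Visit 4 = Day 1, Visit 6 = Day 15, Visit 8 = Day 29, Visit 10 = Day 43, Visit 12 = Day 57, Visit 14 = Day 71 and Visit 16 = Day 85. These match day = 7 × week + 1 (for example, Week 6: 7 × 6 + 1 = 43). The window is ±7 days, with Visit 4 fixed because it defines Day 1. The largest supply per dispensing is 17 days (14 + 3). The plan states no gap between tests, so there is no stated gap to reproduce.

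**Gaps between tests.** Nominal gap = difference in days. Longest gap = latest permitted day of the later visit minus earliest permitted day of the earlier one.

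- Current schedule (Days 1, 43, 85): 43 − 1 = 42 and 85 − 43 = 42. With windows: 50 − 1 = 49 and 92 − 36 = 56.
- Visits 8 and 12 added (Days 1, 29, 43, 57, 85): 28, 14, 14, 28. With windows: 36 − 1 = 35; 50 − 22 = 28; 64 − 36 = 28; 92 − 50 = 42.
- Visits 6, 8, 12 and 14 added: 14 throughout. With windows: 22 − 1 = 21 for the first gap, up to 28 later (for example 36 − 8).

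**Untested dispensings.** The supply given at Visit 4 or Visit 10 follows a test on the same day, so it does not count as untested. Section 2.2.5 limits carry-over: "Subjects will return the previously dispensed study medication at each every other week study visit thereafter".

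| Schedule | Dispensed without a test, per gap | Largest untested supply |
|---|---|---|
| Current | Visits 6 and 8, or 12 and 14 | 2 × 17 = 34 days |
| Visits 8 and 12 added | Visit 6, or Visit 14 | 17 days |
| All four added | none | 0 days |

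**Detection lag.** A urine test turns positive some time after conception. The documents give no lag L; assume a constant value between 0 and 21 days. The longest time from conception on treatment to a positive scheduled test is the nominal gap + L: 42 to 63 days now, 28 to 49 with Visits 8 and 12, and 14 to 35 with all four. L cancels in the comparison, so the worst case shortens by 14 or 28 days at any L in that range.

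**Average wait.** If pregnancies become detectable evenly over Days 1 to 85 (an assumption), the mean wait to the next scheduled test is Σ gap² ÷ (2 × 84):

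- Current: (42² + 42²) ÷ 168 = 3528 ÷ 168 = 21 days.
- Visits 8 and 12 added: (28² + 14² + 14² + 28²) ÷ 168 = 1960 ÷ 168 = 11.7 days.
- All four added: (6 × 14²) ÷ 168 = 1176 ÷ 168 = 7 days.

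**Stopping Rule wording.** The lead-in speaks of two subjects, of one of two conditions and of repeat PK testing, which fits items 1 and 2 only. The closing paragraph counts three events occurring despite dose reduction. Three can be reached in two ways: numbered items 1 to 3, which includes pregnancy; or methemoglobin plus the two separate pressure thresholds inside item 2, which leaves it out. The second fits the reference to dose reduction and to life-threatening events better; the first follows the numbering. The text does not settle which is meant.

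**The case against.** The strongest reply is that no rule is broken. The documents set no interval between tests, so preferring 28 days to 42 is a safety judgement. That stands.

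Safeguards also exist between tests. Section 2.2.4 has phone and in-person contacts alternating weekly with symptom review, and encourages subjects to report concerns at once; menstrual history is taken at Visit 10. These could prompt an unscheduled test, so 42 days is the gap between scheduled tests and not the expected time to recognition. That stands too, though none of these contacts is told to trigger a test.

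A reader might go further than the documents allow in four ways:

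- That one positive test ends the trial. The paragraph describes a pause for review, and the three events can be counted without pregnancy.
- That a pregnant woman would be kept on drug. Item 4 of the same list (compliance) plainly concerns the individual, so item 3 may well mean that she stops. The removed consent pages could also say so. The wording is ambiguous; it does not instruct anyone to continue.
- That nitrite is known to harm the fetus. Section 5.1.1 cites only retrospective case-control associations, with cohort studies showing no significant increase.
- That contraception is not required. Section 3.1.1 refers to specialised criteria for women of child-bearing potential, and Sections 3.2 and 3.3 contain no contraception requirement, but the removed consent pages may. The point does not rest on this.

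**Conclusion.** The point holds as a modest safety improvement, not as an error. The schedule and both 42-day gaps are certain from Section 2.3.2 and Table 1; with windows the gaps can reach 49 and 56 days. At most two dispensings can pass untested after a pregnancy becomes detectable. Adding Visits 8 and 12 takes 14 days off the worst case under any constant detection lag from 0 to 21 days. The average-wait figures depend on the even-spread assumption. How many women this concerns is unknown (0 to 30).

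The Stopping Rule wording is ambiguous in the visible text and needs clarifying whether or not tests are added.

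**What to change.** 1. In Section 2.3.2 and Table 1, add the existing urine pregnancy test for women of child-bearing potential at Visits 8 and 12, before that day's dose and dispensing. Testing at Visits 6 and 14 as well would put a test before every dispensing; since the documents set no interval, that choice is the team's.

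2. In the same amendment, replace item 3 of the Stopping Rule with a subject-level instruction: after a positive test, hold study drug and repeat the test; a confirmed positive permanently stops that subject's study drug. In the closing paragraph, name the three events and state that pregnancy is not among them.

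**Cost.** No new visit is needed. Each woman concerned has 9 tests instead of 7, so at most 2 × 30 = 60 extra strips if all 30 subjects qualified (4 × 30 = 120 with all four visits). There is some added handling, and dosing may pause while a positive is confirmed. If the false-positive rate per test is 0.1% to 1% (an assumption; the documents give none), 60 strips yield at most 0.06 to 0.6 expected false positives and 120 yield 0.12 to 1.2. The two changes should therefore go in together, so that a false positive cannot be read as pausing the study.
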